### 8.3.3 CLINICAL EVALUATION OF NASAL CONGESTION AND TURBINATE HYPERTROPHY

Images, photographic and video, collected at the time of Physical Nasal Exam (See Section 8.3.1) may be evaluated for visible nasal congestion and turbinate hypertrophy by an independent physician reviewer. Images will be collected at the Screening (Visit 1), 1-Month (Visit 5) and 3-Month (Visit 6) Follow-up timepoints.

Images will be of the internal nasal valve only. In the event that only video is collected, still shots will be taken by sponsor showing the internal nasal valve only prior to images being available to physician reviewer. Images to be reviewed are the heads of the inferior and middle turbinate for each side of the nose.

Images will be stored on thumb drives at the individual site, and videos transferred to Sponsor by designated Sponsor representatives via a secure data transfer. Transferred files are not to contain patient health information (“PHI”) data (i.e., name, date of birth, etc.). Files will be identified by the subject's study identification number, the study Visit, and pre- or post-decongestant (e.g., 01-001 V1 pre-decongestant).

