7.2.3 Quantitative nasal endoscopy scores

Endoscopic nasal examinations (before and after decongestant administration) will be performed at baseline and at the 30-day and 90-day follow-up visits. Photos will be taken of the middle and inferior turbinates (before and after decongestant). After deidentification and randomization, an independent physician, blinded to the participant and study visit, will review and grade each photo for 3 findings (inferior turbinate hypertrophy, middle turbinate hypertrophy, and nasal congestion). Each finding will be rated on a scale from 0 (none) to 3 (severe).³ Predecongestant and postdecongestant scores for each finding will be summarized using counts and percentages at baseline and the at the 30-day and 90-day visits.

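### For video-only exams, the sponsor takes the still frames from files named by visit, and neither document masks that step or fixes how the frame is chosen

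*Protocol*

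**What the plan says.** Protocol 8.3.1 lets sites record each nasal exam as video or as images, on both sides, before and after decongestant. Protocol 8.3.3 sets the timing: "Images will be collected at the Screening (Visit 1), 1-Month (Visit 5) and 3-Month (Visit 6) Follow-up timepoints". For exams that yield no photographs, it makes this provision: "still shots will be taken by sponsor showing the internal nasal valve only prior to images being available to physician reviewer".

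The same section has "videos transferred to Sponsor by designated Sponsor representatives via a secure data transfer". It bars personal health information from transferred files and identifies files by "study identification number, the study Visit, and pre- or post-decongestant"; its worked example shows subject number, V1 and pre-decongestant in the name.

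On the view, it limits images to the internal nasal valve and adds: "Images to be reviewed are the heads of the inferior and middle turbinate for each side of the nose".

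SAP 7.2.3 describes the read: "After deidentification and randomization, an independent physician, blinded to the participant and study visit, will review and grade each photo". Each of three findings is scored 0 to 3 and reported as counts and percentages. SAP 3.1.1 lists change in congestion and turbinate hypertrophy on endoscopy as a secondary endpoint.

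**The concern.** Masking a grader protects the grading step only. If the material being graded was picked earlier by someone who knew which visit it came from, the picking can carry a preference that the grader cannot see or undo. A video offers many frames, which can differ in angle and distance, and the grade has only four levels.

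This matters more than it would in a controlled trial. The study is open-label with no control arm, and this read is the one efficacy outcome where someone without knowledge of the visit makes the judgement. The extraction step sits with the sponsor, which has an interest in the result.

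**Working it through.** The documents state no figure on this point, so the check is mainly a comparison of texts.

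**1. When the step applies.** Only when an exam produced video and no photographs (Protocol 8.3.3). Where sites supply photographs, the sponsor chooses no frame. Protocol 8.3.1 allows either format, so the video-only share is open.

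**2. What the extractor could see.** The file name gives subject and visit. Visit 1 is before treatment; Visits 5 and 6 are after it. The name therefore reveals treatment status. The decongestant label does not.

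**3. Whom the blinding covers.** SAP 7.2.3 names one masked person, the grading physician. Neither document says that the extractor is masked, and neither gives a frame rule beyond the view to be shown.

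**4. Order of steps.** Protocol 8.3.3 puts extraction before the reviewer receives images. SAP 7.2.3 puts de-identification and randomisation before grading. Neither orders extraction against de-identification. The SAP speaks of photos and does not mention video in that section; for a video-only exam, the photo exists only once a still has been taken. The natural reading is extraction first, but it is an inference.

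**5. Other efficacy outcomes.** rTNSS, NOSE, SNOT-22, VAS, MiniRQLQ and procedural pain are reported by participants who know they were treated. CGI-I and the on-site exam are scored by site clinicians in an open-label study. None has a blinded assessor.

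**6. Ceiling on exposure.** Captures per participant = 3 visits × 2 sides × 2 decongestant states = 12. With 30 participants all attending, 12 × 30 = 360. The number exposed is 360 × p, where p is the video-only share: 0 at p = 0 and 360 at p = 1.

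**7. Scale of a possible shift (illustration only).** Suppose the most favourable of k usable frames were always taken at follow-up, with frame-to-frame standard deviation s on the 0–3 scale treated as numeric. The mean change would shift by E(k) × s × p, where E(k) is the expected largest of k independent standard normal values: E(3) = 0.846, E(5) = 1.163. The values of k, s and p are assumptions, not taken from the documents.

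- Low end: k = 3, s = 0.2, p = 0.25 gives 0.846 × 0.2 × 0.25 = 0.04 points.
- High end: k = 5, s = 0.4, p = 1 gives 1.163 × 0.4 × 1 = 0.47 points.
- If the least favourable frame were also taken at baseline, these double to about 0.08 and 0.93 points.

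This describes consistent one-directional choosing, so it is an upper-type scenario. Without a consistent direction in the choice, or with no video-only exams, the shift is zero.

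**The case against.** The strongest reply is that the plan describes no unblinded selection. The sponsor may intend to recode the videos before extraction, and nothing forbids it. Extraction is a fallback, since the SAP speaks of photos being taken at each exam. The required view also limits which frames qualify. Little rests on the result: the protocol makes the independent read optional, SAP 7.2.3 reports it descriptively, Protocol 9.4.7 treats visual severity as exploratory, and the study is a feasibility study with a convenience sample and a safety primary endpoint. Site staff who take photographs also know the visit, so capture is never fully masked.

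Most of this stands, and it limits the weight of the point. It does not close the gap: if recoding first is intended, neither document says so. A required view narrows the choice of frame but does not settle it. Choice at capture is hard to avoid, whereas a second choice at the sponsor is easy to mask. A descriptive shift table is biased if the frames behind it are. Protocol 9.4.3 also lists physician assessments of congestion and hypertrophy among endpoints for a Wilcoxon signed rank test, without saying whether it means the site grade or the independent read.

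A reader might infer three stronger things. First, that sponsor staff do choose frames knowing treatment status: the documents leave this possible but do not state it. Second, that all graded images are affected: the step is conditional on video-only capture. Third, that frame choice moves a score by a whole grade: nothing in the documents supports a shift of that size. One might also see a contradiction between the nasal valve and the turbinate heads; the two can be read as where the view is taken and what is graded, so this needs only a clarification.

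**Conclusion.** The gap is real but limited. For video-only exams, the plan lets stills be taken from files that reveal treatment status, by someone it does not mask and without a frame rule, so blinding the grader may not prevent selection bias. The size cannot be derived from the documents, because the video-only share and the variation between frames are not given.

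The conclusion rests on file names being visible at extraction, which is the natural reading but not stated. It should be corrected before images are read, because it touches the one blinded efficacy outcome. It does not threaten the trial's main conclusions.

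**What to change.** In Protocol 8.3.3 and SAP 7.2.3, put the planned de-identification and randomisation ahead of still extraction:

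- Recode each video so that subject number and visit are removed before any still is taken. The decongestant label can stay, because it does not show treatment status and the two states are summarised separately.
- Have the stills taken by someone who does not hold the key, under a fixed rule, for example the first in-focus frame showing the heads of the inferior and middle turbinates. This also settles the target view.
- Report the share of stills derived from video, by visit.

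Letting the blinded physician choose frames from full video is less attractive: Protocol 8.3.1 has treated sites graded for bleeding, crusting and swelling at Visits 5 and 6, so wider footage could reveal the visit.

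The cost is a small file-recoding task and a key held apart from the extractor. No new visit, reader or participant procedure is needed. Masking of the extractor may remain incomplete where the footage itself shows treatment changes, and the report should say so.

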## 8.4 ADVERSE EVENTS, ADVERSE DEVICE EFFECTS, SERIOUS ADVERSE EVENTS AND UNEXPECTED ADVERSE DEVICE EFFECTS

In this study, the following types of adverse events will be collected and documented:

- ClariFix Device-related Adverse Device Effects (ADE)
- Cryotherapy procedure-related Adverse Events (AE)
- Head, ear, nose, throat, and breathing/lung related AEs, including anticipated AEs
- All Serious Adverse Events (SAE)
- Unanticipated Adverse Device Effects (UADE)

Anticipated adverse events are identified in the ClariFix IFU (See Appendix I).

### 8.4.1 DEFINITION OF ADVERSE EVENTS (AE)

An adverse event (AE) is any untoward medical occurrence in a subject who receives treatment with the study device, which does not necessarily have a causal relationship with this treatment. An adverse event (AE) can therefore be any unfavorable and unintended sign, symptom, or disease temporally associated with the treatment with the study device, whether or not related to the treatment or device.

All AEs must be reported to the study sponsor.

### 8.4.2 DEFINITION OF ADVERSE DEVICE EFFECT (ADE)

Any adverse event related to the use of the study device. An adverse event is an untoward medical occurrence, unintended disease or injury, or untoward clinical sign in subjects.

### 8.4.3 DEFINITION OF SERIOUS ADVERSE EVENTS (SAE)

An adverse event (AE) or suspected adverse reaction is considered "serious" if, in the view of either the investigator or sponsor, it results in any of the following outcomes: death, a life-threatening adverse event, inpatient hospitalization or prolongation of existing hospitalization, a persistent or significant incapacity or substantial disruption of the ability to conduct normal life functions, or a congenital anomaly/birth defect. Important medical events that may not result in death, be life-threatening, or require hospitalization may be considered serious when, based upon appropriate medical judgment, they may jeopardize the participant and may require medical or surgical intervention to prevent one of the outcomes listed in this definition.

### 8.4.4 DEFINITION OF UNEXPECTED ADVERSE DEVICE EFFECT (UADE)

Any serious adverse effect on health or safety or any life-threatening problem or death caused by, or associated with, the study device, if that effect, problem or death was not previously identified in nature, severity or degree of incidence in the investigational plan or application (including a supplementary plan or application), or any other unanticipated, serious problem associated with a device that relates to the rights, safety or well-being of subjects.

### 8.4.5 CLASSIFICATION OF AN ADVERSE EVENT

#### 8.4.5.1 SEVERITY OF EVENT

For all adverse events (AEs), the following guidelines will be used to describe severity.

- **Mild** – Events require minimal or no treatment and do not interfere with the participant’s daily activities.
- **Moderate** – Events result in a low level of inconvenience or concern with the therapeutic measures. Moderate events may cause some interference with functioning.
- **Severe** – Events interrupt a participant’s usual daily activity and may require systemic drug therapy or other treatment. Severe events are usually potentially life-threatening or incapacitating. Of note, the term “severe” does not necessarily equate to “serious”.

---

#### 8.4.5.2 RELATIONSHIP TO STUDY INTERVENTION

All adverse events (AEs) must have their relationship to both the study device and study procedure assessed by the clinician who examines and evaluates the subject based on temporal relationship and his/her clinical judgment. The degree of certainty about causality will be graded using the categories below. In a clinical trial, the study product must always be suspect.

- **Definitely Related** – There is clear evidence to suggest a causal relationship to either the study device or the study procedure, and other possible contributing factors can be ruled out. The clinical event, including an abnormal laboratory test result, occurs in a plausible time relationship to study device or the study procedure and cannot be explained by concurrent disease or other drugs or chemicals. The event must be phenomenologically definitive.
- **Probably Related** – There is evidence to suggest a causal relationship to either the study device or the study procedure, and the influence of other factors is unlikely. The clinical event, including an abnormal laboratory test result, occurs within a reasonable time after administration of the study intervention, is unlikely to be attributed to concurrent disease or other drugs or chemicals.
- **Potentially Related** – There is some evidence to suggest a causal relationship to either the study device or the study procedure (e.g., the event occurred within a reasonable time after study procedure). However, other factors may have contributed to the event (e.g., the participant’s clinical condition, other concomitant events).
- **Unlikely to be related** – A clinical event, including an abnormal laboratory test result, whose temporal relationship to either the study device or the study procedure makes a causal relationship improbable (e.g., the event did not occur within a reasonable time after study procedure) and in which other drugs or chemicals or underlying disease provides plausible explanations (e.g., the participant’s clinical condition, other concomitant treatments).
- **Not Related** – The AE is completely independent of either the study device or the study procedure, and/or evidence exists that the event is definitely related to another etiology. There must be an alternative, definitive etiology documented by the clinician.

---

#### 8.4.5.3 EXPECTEDNESS

Sponsor will be responsible for determining whether an adverse event (AE) is expected or unexpected. An AE will be considered unexpected if the nature, severity, or frequency of the event is not consistent with the risk information previously described for the study intervention.

---

#### 8.4.6 TIME PERIOD AND FREQUENCY FOR EVENT ASSESSMENT AND FOLLOW-UP

The occurrence of an adverse event (AE), adverse device effect (ADE) or serious adverse event (SAE) may come to the attention of study personnel during study visits and interviews of a study participant presenting for medical care, or upon review by a study monitor.

Information to be collected includes event description, time of onset, clinician's assessment of severity, relationship to study product (assessed only by those with the training and authority to make a diagnosis), and time of resolution/stabilization of the event. All AEs occurring while on study must be documented appropriately regardless of relationship. All AEs will be followed to adequate resolution.

Any medical condition that is present at the time that the participant is screened will be considered as baseline and not reported as an AE. However, if the study participant's condition deteriorates at any time during the study, it may be recorded as an AE.

Changes in the severity of an AE will be documented to allow an assessment of the duration of the event at each level of severity to be performed. AEs characterized as intermittent require documentation of onset and duration of each episode.

Study site will record all reportable events with start dates occurring any time from treatment with the study device until 7 (for non-serious AEs) or 30 days (for SAEs) after the last day of study participation. At each study visit, the investigator will inquire about the occurrence of AE/SAEs since the last visit. Events will be followed for outcome information until resolution or stabilization.]

---

#### 8.4.7 ADVERSE EVENT REPORTING

AEs should be documented in the source documents at time of identification, and initial entry of all AEs into the EDC should be completed within 72 hours of identification. Initial EDC entry may be pending additional information, but known information should be entered. Source and EDC entry should be updated as new information becomes available and upon resolution of the AE.

Additionally, Sponsor must be notified of SAE, SADE and UADE within 24-hours of identification via phone or email.

---

#### 8.4.8 SERIOUS ADVERSE EVENT REPORTING

The study investigator shall complete an Adverse Event source form and email a copy of the form to sponsor within 24-hours of identification, in addition the AE reporting in section 8.4.7 should be followed. If IRB notification is required, this should be completed as soon as possible, but in no event later than 10 working days after the investigator first learns of the effect.

In the event of an unanticipated adverse device effect, the study sponsor is responsible for conducting an evaluation of any and shall report the results of such evaluation to the Food and Drug Administration (FDA) and to all reviewing IRBs and participating investigators within 10 working days after the sponsor first receives notice of the effect. Thereafter, the sponsor shall submit such additional reports concerning the effect as FDA requests.

## 9 STATISTICAL CONSIDERATIONS

### 9.1 STATISTICAL HYPOTHESES

Primary Efficacy Endpoints:

H0: Change from Baseline (Delta) in rTNSS = 0

H1: Change from Baseline (Delta) in rTNSS  $\neq$  0

Secondary Efficacy Endpoints:

H0: Change from Baseline (Delta) = 0

H1: Change from Baseline (Delta)  $\neq$  0

## 9.2 SAMPLE SIZE DETERMINATION

Inasmuch as this is a feasibility study with N=30, no formal power and/or sample size estimations were performed. The proposed sample size is comparable to those in other trials of this nature in this discipline.

## 9.3 POPULATIONS FOR ANALYSES

There are two key populations for analyses:

- The Safety Population is comprised of those subjects who received treatment by the ClariFix device
- The Efficacy Population is comprised of those subjects in the Safety Population who also had at least one valid follow-up assessment.

## 9.4 STATISTICAL ANALYSES

### 9.4.1 GENERAL APPROACH

All statistical analyses will be performed using a two-sided hypothesis test at the overall 5% level of significance. P-values will be rounded to three decimal places. If a p-value is less than 0.001 it will be reported as "< 0.001." If a p-value is greater than 0.999 it will be reported as "> 0.999." No adjustments for multiplicity are planned.

Continuous data will be summarized using descriptive statistics: n, mean, standard deviation or standard error, median, minimum and maximum. The decision to use either standard deviation or standard error will be based upon the objective of the presentation: standard deviation will be used when the interest is the natural variability of the data; standard error will be used when comparing two or more means. Continuous variables that are recorded using approximate values (e.g., < or >) will be replaced by the closest exact value for the calculation of summary statistics.

Categorical variables will be summarized using frequency counts and percentages.

For ordinal-scaled variables, a combination of the above may be employed as appropriate: frequency and percentage of observations within a category and means and standard deviations of the scores of the categories.

For categorical and ordinal variables, percentages will be calculated based on non- missing data.

All analyses will be based on available data; no imputation for missing data will be conducted.

Baseline is defined as the last measurement for the outcome of interest obtained before the exposure to the study device.

Duration variables will be calculated using the general formula: [(end date – start date) +1]

Within-subject changes will be calculated as visit value minus baseline value such that a negative change reflects a decrease and a positive change signifies an increase. No judgment (“better” or “worse”) is associated with the sign of the change, only direction. The Wilcoxon Signed Rank test will be used to test the null hypothesis that the mean (or median) within-subject change is equal to zero.

---

#### 9.4.2 ANALYSIS OF THE PRIMARY EFFICACY ENDPOINT(S)

For the purposes of formality, rTNSS has been designated as the primary efficacy endpoint. However, since this is, in fact, a feasibility study, any of the secondary endpoints described below may be promoted in the next study to primary status. Therefore, the analytical approach for all efficacy endpoints will be identical.

The objective of these analyses is to present the changes from baseline for a small sample size in a manner that is statistically sound and intuitively comprehensible. To that end the tables will present summary statistics for the Baseline, 7-Day, and 1- and 3-Month timepoints, as well as serial changes from baseline.

The statistical null hypothesis is that the deltas are distributed around zero change. Wilcoxon Signed Rank tests will be employed to evaluate whether the deltas are distributed around zero or shifted either positively or negatively away from zero. No adjustments for multiplicity are planned since this is a feasibility or proof of concept study.

---

#### 9.4.3 ANALYSIS OF THE SECONDARY ENDPOINT(S)

The secondary endpoints are changes over time in:

- NOSE Survey
- SNOT-22
- MiniRQLQ
- VAS – nasal symptoms
- CGI-I
- Physician Assessment of congestion
- Physician Assessment of turbinate hypertrophy

The analytical approach is described in the section above for the Primary Endpoint.

---

#### 9.4.4 SAFETY ANALYSES

The overall incidence (i.e., number and percent of subjects with 1 or more adverse event) of adverse events, serious adverse device events, serious adverse events, and device and/or procedure related events (e.g., possibly, probably or definitely related) will be calculated from time of treatment through the entire duration of follow-up. The overall incidence of mild, moderate and severe events will be calculated by considering the most severe event for each subject.

In addition, the overall incidence for each adverse event type will be calculated. The adverse event types will be classified as defined in Section 8.4.

---

